7.4.1.3 Cumulative Dose, Dose Intensity, and Relative Dose Intensity

In order to compute the cumulative dose of dexamethasone, IV dexamethasone will have to be converted to its equivalent oral dose. This will be done by treating each mg of IV dexamethasone as 1.32 mg of oral dexamethasone, i.e. making use of the fact that the mean bioavailability of oral dexamethasone was estimated to be 0.76¹⁰. A subject’s cumulative dose of dexamethasone will be defined as the sum of all dexamethasone doses, oral and IV, converted to oral equivalent. The cumulative dose administered will be summarized for each of these drugs, by treatment group.

Elotuzumab:

A subject’s cumulative dose of elotuzumab is measured in mg/kg, and is defined as the sum of their elotuzumab doses (mg/kg) (actual, not planned) over all infusions.

Elotuzumab dose intensity (mg/kg/week) per subject will be calculated separately for Cycles 1 and 2, Cycles 3-18 and Cycle 19 and beyond, since elotuzumab planned dose intensity differ in those cycles.

Cycle 1 and 2

$$7 \times \left(\frac{\text{cumulative dose of elotuzumab during the first 2 cycles}}{\left(\frac{\min(\text{date of first dose of elotuzumab in the last cycle among the first 2 cycles} + 28, \text{death date}) - \text{date of first dose of elotuzumab in Cycle 1}}{\text{date of first dose of elotuzumab in Cycle 1}} \right)} \right)$$

Cycle 3-18:

$$7 \times \left(\frac{\text{cumulative dose of elotuzumab during Cycle 3 – Cycle 18}}{\left(\frac{\min(\text{date of first dose of elotuzumab in last cycle among 18 cycles} + 28, \text{death date}) - \text{date of first dose of elotuzumab in Cycle 3}}{\text{date of first dose of elotuzumab in Cycle 3}} \right)} \right)$$

Cycle 19 and beyond:

$$7 \times \left(\frac{\text{cumulative dose of elotuzumab starting from Cycle 19}}{\left(\frac{\min(\text{date of first dose of elotuzumab in last cycle} + 28, \text{death date}) - \text{date of first dose of elotuzumab in Cycle 19}}{\text{date of first dose of elotuzumab in Cycle 19}} \right)} \right)$$

The relative dose intensity will be calculated as

$$\text{Dose Intensity/Planned Dose Intensity (PDI)}$$

Planned dose per week for elotuzumab is 10mg/kg/week for the first 2 cycles, 5mg/kg/week for cycles 3 and beyond. The PDI per subject for elotuzumab will be computed by averaging the planned doses per week over the treatment duration:

$$\text{Elotuzumab PDI (mg/kg/wk)} = \frac{(\text{DOSE1} * 8 + \text{DOSE2} * (\text{DUR} - 8))}{\text{DUR}}$$

where DUR is defined as (min (date of death, date of first dose in last cycle in timepoint + 28) - date of first dose in timepoint) / 7.

Dose intensity and relative dose intensity of elotuzumab will be summarized for the E-Ld group only.

Lenalidomide:

A subject's cumulative dose of lenalidomide is defined as the sum of each dose taken, as recorded in their medication diary.

Dose intensity and relative dose intensity for lenalidomide (mg/week) will be calculated separately for subjects who began the study at the standard daily dose, 25mg/day and those who, because of moderate renal impairment, began the study at < 25mg/day (at 10mg/day dose will be assumed when computing the RDI as this is the recommended dose for subject with moderate renal disease per protocol).

The lenalidomide dose intensity, per subject, will be calculated as:

$$7 \times \left(\frac{\text{cumulative dose of lenalidomide}}{(\text{min}(\text{date of 1st dose of lenalidomide in last cycle in which lenalidomide was administered}) + 28, \text{death date}) - \text{date of first dose of lenalidomide}} \right)$$

The relative dose intensity of lenalidomide is the dose intensity per week divided by the planned dose intensity per week, 131.25mg (or 52.5mg for subjects who begin therapy at < 25mg (10mg/day per protocol)).

Dexamethasone:

The dose intensity (mg/week) of dexamethasone, per subject, will be calculated separately for the period encompassing Cycles 1 and 2, Cycle 3-18 and Cycle 19 and beyond since dexamethasone dosing is different in these 3 periods.

Cycle 1 and 2:

$$7 \times \left(\frac{\text{cumulative dose of dexamethasone during the first two cycles}}{(\text{min}(\text{date of first dose of dexamethasone in last cycle among first 2 cycles} + 28, \text{death date}) - \text{date of first dose of dexamethasone in first cycle})} \right)$$

Cycle 3-18:

$$7 \times \left(\frac{\text{cumulative dose of dexamethasone during Cycle 3 - Cycle 18}}{(\text{min}(\text{date of first dose of dexamethasone in last cycle among 18 cycles} + 28, \text{death date}) - \text{date of first dose of dexamethasone in Cycle 3})} \right)$$

Cycle 19 and beyond:

$$7 \times \left(\frac{\text{cumulative dose of dexamethasone starting from Cycle 19}}{\left(\min(\text{date of first dose of dexamethasone in last cycle} + 28, \text{death date}) - \right) \text{date of first dose of dexamethasone in Cycle 19}} \right)$$

The relative dose intensity of dexamethasone is the dose intensity per week divided by the planned dose intensity per week. The planned dose of dexamethasone in the experimental arm on elotuzumab dosing days, 8mg IV dexamethasone plus 28mg oral dexamethasone, is equivalent to 38.56mg of oral dexamethasone. The planned dose in the experimental arm when dexamethasone is not being administered with elotuzumab is 40mg. Thus, the planned weekly dose of dexamethasone in the experimental arm for Cycles 1 and 2 will be equivalent to 38.56mg oral dexamethasone, the planned weekly dose of dexamethasone in the experimental arm for Cycle 3 - Cycle 18, during which IV dexamethasone is given on Days 1 and 15 only, will be equivalent to 39.28mg of oral dexamethasone and the planned weekly dose of dexamethasone in the experimental arm for Cycle 19 and beyond, during which IV dexamethasone is given on Days 1 only, will be equivalent to 39.64mg of oral dexamethasone . The planned weekly dose of dexamethasone in the control arm is 40mg for all cycles.

In the dose intensity formulas, if the patient took a dose on his death date then 1 day will be added to the denominator.

Descriptive statistics (n, mean, STD, median, min, max, q1 and q3) will be presented for the cumulative dose, and dose intensity of each agent, by treatment group. The number and percentage of subjects whose relative dose intensity falls into the following categories will be presented, by treatment group: ≥ 90 %, 80% to < 90%, 70% to < 80%, 60% to < 70%, < 60%.

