6.2 Treatment Regimens

Subjects will be randomized to one of two treatment arms, E-Ld or Ld. Subjects will receive these treatments in 28-day cycles until disease progression, unacceptable toxicity or withdrawal of consent.

On Arm A (E-Ld) subjects receive:

- Elotuzumab: 10 mg/kg intravenous (IV) on Days 1, 8, 15 and 22 of the cycle during Cycles 1 and 2; Days 1 and 15 during Cycles 3-18; and 20mg/kg intravenous (IV) on Day 1 of the cycle during subsequent cycles.
- Lenalidomide: 25 mg orally (po) on Days 1-21 of each cycle.
- Dexamethasone: Administered on Days 1, 8, 15 and 22 of cycle. 28 mg po + 8 mg IV whenever given prior to elotuzumab; 40 mg po on weeks on which no elotuzumab is given.

On Arm B (Ld) subjects receive:

- Lenalidomide: 25 mg po on Days 1-21 of each cycle.
- Dexamethasone: 40 mg po on Days 1, 8, 15 and 22 of each cycle.

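### The dose-intensity formulas have no rule for a cycle still open at data cut-off, so adherent ongoing subjects are reported as under-dosed, mainly for dexamethasone in Cycle 19 and beyond at the interim analysis

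*SAP*

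**What the plan says.** SAP Section 7.4.1.3 defines dose intensity as seven times the cumulative dose divided by an interval in days. For dexamethasone the interval ends at the earlier of the "date of first dose of dexamethasone in last cycle" plus 28 days and the death date. The calculation is made "separately for the period encompassing Cycles 1 and 2, Cycle 3-18 and Cycle 19 and beyond".

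For lenalidomide there is one calculation over all treatment. It ends at the "date of 1st dose of lenalidomide in last cycle in which lenalidomide was administered" plus 28 days, or at death. Elotuzumab uses the same end rule in the same three periods as dexamethasone.

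The only adjustment given is for death: "In the dose intensity formulas, if the patient took a dose on his death date then 1 day will be added to the denominator". Data cut-off does not appear in these formulas, although SAP Section 7.5.10 uses it for currentness of follow-up.

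RDI is dose intensity divided by planned dose intensity. It is tabulated by arm in five categories, from 90% or more down to below 60%. SAP Section 8.7 lists the dose-intensity summaries for all three drugs among the topline outputs.

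**The concern.** Treatment continues until progression, so many subjects will be part-way through a cycle at any PFS cut-off. The numerator then holds only the doses taken so far, while the denominator already contains the whole 28 days. The SAP shortens the last cycle for a subject who dies but not for one whose data stop at the snapshot.

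Dexamethasone in Cycle 19 and beyond is the most exposed. The count restarts at Cycle 19, so a subject who has just entered that period has few or no completed cycles to dilute the shortfall. A topline table of backbone delivery would then place fully adherent subjects in low RDI categories because of the calendar. It would also lower the reported means, first quartiles and minima.

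**Working it through.** **1. Reproduce the plan's own figures.** SAP Section 7.4.1.3 counts 1 mg IV as 1.32 mg oral.
- Elotuzumab days: 28 + 8 × 1.32 = 38.56 mg, as stated ("8mg IV dexamethasone plus 28mg oral dexamethasone, is equivalent to 38.56mg of oral dexamethasone").
- E-Ld, Cycles 3–18: (2 × 38.56 + 2 × 40)/4 = 39.28 mg/week. Cycle 19 and beyond: (38.56 + 3 × 40)/4 = 39.64 mg/week.
- Control: "The planned weekly dose of dexamethasone in the control arm is 40mg for all cycles".
- Lenalidomide: 25 × 21/4 = 131.25 mg/week.

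All match the SAP. With every cycle complete, the formulas return exactly 100% for an adherent subject, so the open cycle is the only source of shortfall.

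**2. Dexamethasone in an open cycle.** The control schedule is "Dexamethasone: 40 mg po on Days 1, 8, 15 and 22 of each cycle". Let k be the number of cycles started in the period and n the doses taken in the open one. For full adherence, RDI = 1 − (4 − n)/(4k).

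| Cycle (k) | n = 1 | n = 2 | n = 3 | n = 4 |
|---|---|---|---|---|
| 19 (1) | 25% | 50% | 75% | 100% |
| 20 (2) | 62.5% | 75% | 87.5% | 100% |
| 21 (3) | 75% | 83.3% | 91.7% | 100% |
| 23 (5) | 85% | 90% | 95% | 100% |
| 25 (7) | 89.3% | 92.9% | 96.4% | 100% |
| 26 (8) | 90.6% | 93.8% | 96.9% | 100% |

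For example, one dose in Cycle 19 gives 7 × 40/28 = 10 mg/week, and 10/40 = 25%. E-Ld values are at most 0.7 points lower (24.3%, 49.5% and 74.8% in Cycle 19). A false RDI below 90% is possible only in Cycles 19–25. A cut-off on Days 22–28 produces no error.

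**3. Who is exposed at the interim (about month 41, Protocol Section 8.5).** Accrual of 750 at 24 per month takes 31.25 months, so the last subject has 9.75 months of follow-up and is in Cycle 11.
- No ongoing subject is in Cycles 1–2.
- Ongoing subjects in Cycles 3–18 have k ≥ 9, so dexamethasone RDI is at least 91.6%.
- Lenalidomide: RDI = 1 − (21 − min(d, 21))/(21k) on day d of the open cycle. With k ≥ 11 the lowest value is 1 − 20/231 = 91.3%.
- Elotuzumab, Cycles 3–18, k = 9, one of two doses taken: 17/18 = 94.4%. From Cycle 19 its single Day 1 dose covers the cycle, so RDI is 100%.

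**4. How many subjects.** Assumptions: 12 subjects per month per arm; exponential time on treatment with the protocol's PFS medians (25 and 33.75 months); treatment stops only at a PFS event; full adherence. As a check on the timeline, this model gives 332 events at month 41 and 484 at month 60, against the planned 338 and 482.
- One cycle is 28/30.4375 = 0.920 months, so Cycle 19 starts at 16.56 months. The fraction randomized early enough is (41 − 16.56)/31.25 = 0.782.
- Reaching Cycle 19: Ld 375 × 0.782 × 2^(−16.56/25) = 185; E-Ld 375 × 0.782 × 2^(−16.56/33.75) = 209.
- Hand check, Ld below 90%: each cycle of follow-up holds 12 × 0.920 = 11.04 randomized subjects. The affected shares of cut-off days for k = 1 to 7 are 75, 75, 50, 50, 25, 25 and 25%. Weighting by mid-cycle survival (0.624 falling to 0.535) gives a sum of 1.92, and 11.04 × 1.92 = 21.2. Full integration gives 21.3.

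| Month 41, Cycle 19 and beyond | Ld | E-Ld |
|---|---|---|
| Reached Cycle 19 | 185 | 209 |
| Falsely below 90% | 21.3 (11.5%) | 26.2 (12.6%) |
| Falsely below 60% | 3.5 (1.9%) | 3.9 (1.9%) |
| Mean understatement, points | 4.8 | 5.0 |

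**5. Final PFS analysis (about month 60).** The shortest follow-up is 28.75 months, which is Cycle 32, so k ≥ 14. Dexamethasone RDI in this period is then at least 94.6% and lenalidomide at least 97.0%. No adherent subject leaves the top category.

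**6. Capping at the cut-off date does not work.** In Cycle 19 on Day 10, 7 × 80/10 = 56 mg/week, an RDI of 140%; on Day 8 it is 175%. A subject in the first lenalidomide cycle, cut off on any of Days 1–21, has 7 × 25/131.25 = 133%.

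**The case against.** The strongest objection is that this changes little that anyone would act on. The outputs are descriptive. Category errors are confined to one drug, one of its three reporting periods, seven cycles and the interim. Under SAP Section 2.3 the study team has no randomization codes, and the DMC tells the sponsor to unblind PFS only if the boundary is met, so sponsor tables by arm at month 41 arise only after a positive interim. All of this stands and limits the weight of the point. But a positive interim is exactly when those tables would describe drug delivery in support of the result.

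A reader might infer that E-Ld, with more subjects still on treatment, would falsely show poorer dexamethasone delivery. The figures do not support that. More E-Ld subjects are ongoing, but more also reach Cycle 19, so the percentages hardly differ. Most of the one-point gap at the 90% cut is an edge case: in Cycle 23 with two doses taken, RDI is 90.0% in Ld and 89.9% in E-Ld. If both arms are classified by the control-arm values, the shares are 11.5% and 11.7%.

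Two further objections stand in part. The 25% figure needs a cut-off in Days 1–7 of Cycle 19 and is an extreme. The documents also do not say how records from an open cycle enter the analysis data. If only completed cycles are extracted, the artefact disappears, but the SAP should then say so.

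**Conclusion.** The point holds as a limited, descriptive defect. The rule as written misstates RDI for adherent subjects in mid-cycle at cut-off. It matters mainly for dexamethasone in Cycle 19 and beyond at the interim, where about 12% of subjects reaching that period in each arm would be falsely below 90%.

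These counts rest on full adherence, treatment stopping only at a PFS event, and dose records being complete to the cut-off day. Earlier discontinuation for other reasons would lower the number of ongoing subjects affected; the per-subject RDI values in the table do not depend on that assumption.

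The documents do not support a claim of between-arm distortion, of category changes at the final PFS analysis, or of an adherent lenalidomide subject falling below 90% at either analysis. Correcting lenalidomide and elotuzumab is for consistency. No test, boundary or endpoint depends on these summaries.

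**What to change.** Add one rule to SAP Section 7.4.1.3 for dexamethasone, lenalidomide and elotuzumab alike: for a subject still receiving the drug at data cut-off, leave the cycle in progress out of both the cumulative dose and the interval. Adherent subjects then score 100%. If the analysis data already hold completed cycles only, a sentence saying so is enough.

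An alternative is to count as planned only the doses scheduled up to cut-off. That corrects RDI but leaves the mg/week dose intensity understated, so the first option is cleaner. The denominator should not simply be capped at the cut-off date.

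The cost is a short SAP edit and a small programming change. Under the first option, ongoing subjects with no completed cycle in a period drop out of that period's summary, while subjects who stopped in the same cycle remain. That is a mild selection, and the number omitted should be reported by arm. For dexamethasone in Cycle 19 and beyond at month 41 it is about 7 of 185 in Ld and 8 of 209 in E-Ld. These are twice the counts below 60%, because RDI below 60% arises only in Cycle 19 with one or two of the four doses taken, which is half of the cut-off days.

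### Dose-intensity denominators in SAP 7.4.1.3 stop at death while each dose counts in full, so deaths soon after a period's first dose inflate reported dose intensity (minor)

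*SAP*

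**What the plan says.** SAP 7.4.1.3 computes dose intensity (DI) as 7 × cumulative dose ÷ days. The days run from the first dose of the period to the earlier of death and 28 days after the first dose of the last cycle. The same cut at death appears in DUR, the duration used for planned elotuzumab intensity: "min (date of death, date of first dose in last cycle in timepoint + 28) - date of first dose in timepoint) / 7". Cumulative dose is the plain sum of doses taken.

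Elotuzumab DI "will be calculated separately for Cycles 1 and 2, Cycles 3-18 and Cycle 19 and beyond, since elotuzumab planned dose intensity differ in those cycles". Dexamethasone is split in the same way; lenalidomide has one clock for the whole of treatment. One special rule covers death: "In the dose intensity formulas, if the patient took a dose on his death date then 1 day will be added to the denominator".

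The weekly plans are stated: "Planned dose per week for elotuzumab is 10mg/kg/week for the first 2 cycles, 5mg/kg/week for cycles 3 and beyond" and "The planned weekly dose of dexamethasone in the control arm is 40mg for all cycles". The schedule in SAP 6.2 is "Elotuzumab: 10 mg/kg intravenous (IV) on Days 1, 8, 15 and 22 of the cycle during Cycles 1 and 2", then "Days 1 and 15 during Cycles 3-18; and 20mg/kg intravenous (IV) on Day 1 of the cycle during subsequent cycles".

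DI is summarised by mean, standard deviation, median, minimum, maximum and quartiles. Relative dose intensity (RDI) is tabulated only in categories, the top one open-ended from 90%. SAP 8.7 lists the dose-intensity summary for each of the three drugs among the topline outputs.

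**The concern.** Each dose is meant to cover an interval: 7 days for dexamethasone and for elotuzumab in Cycles 1-2, 14 days for elotuzumab in Cycles 3-18, and 28 days from Cycle 19. If the subject dies inside that interval, the numerator keeps the whole dose while the denominator keeps only the days lived. Weekly intensity is then generally overstated. The overstatement is largest just after a clock restart, when no earlier time dilutes it.

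It falls only on subjects who die within 28 days of the first dose of their last cycle, whose exposure is likely to be examined closely. A DI of 140 mg/kg/week against a plan of 5 would look like a dosing or data error. A subject who missed doses shortly before death could also be shown as having received at least 90% of plan.

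**Working it through.** **1. Reproduce the plan (28-day cycles).**
- Elotuzumab per week: 4 × 10 ÷ 4 = 10; 2 × 10 ÷ 4 = 5; 1 × 20 ÷ 4 = 5 mg/kg.
- Dexamethasone, E-Ld: 28 + 8 × 1.32 = 38.56 mg; (2 × 38.56 + 2 × 40) ÷ 4 = 39.28; (38.56 + 3 × 40) ÷ 4 = 39.64.
- Lenalidomide: 25 × 21 ÷ 4 = 131.25 mg.

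All match the SAP. For a fully dosed survivor the DI formulas return 10, 5 and 5 mg/kg/week, so they work when no death intervenes.

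**2. Death d days after a period's first elotuzumab dose, adherent subject.** Multiple of plan = [7 × dose given ÷ (d, plus 1 if a dose was given on the death date)] ÷ planned weekly dose.

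| d | Cycles 1-2 | Cycle 3 | Cycle 19 |
|---|---|---|---|
| 0 (denominator 0 + 1) | 7.00 | 14.00 | 28.00 |
| 1 | 7.00 | 14.00 | 28.00 |
| 3 | 2.33 | 4.67 | 9.33 |
| 6 | 1.17 | 2.33 | 4.67 |
| 7 | 1.75 (second dose given) | 2.00 | 4.00 |
| 13 | 1.08 | 1.08 | 2.15 |
| 27 | 1.04 | 1.04 | 1.04 |

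Example, Cycle 19, d = 0: 7 × 20 ÷ 1 = 140 mg/kg/week; 140 ÷ 5 = 28.

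**3. Other drugs.** Dexamethasone on a period's first day: 7 × 38.56 ÷ 38.56 = 7.00, 7 × 38.56 ÷ 39.28 = 6.87 and 7 × 38.56 ÷ 39.64 = 6.81 in E-Ld; 7 × 40 ÷ 40 = 7.00 in Ld. Lenalidomide up to Day 21 of Cycle 1: 7 × 25 ÷ 131.25 = 1.33. Its clock does not restart, so by Day 21 of Cycle 12 it is (7 × 25 × 252 ÷ 329) ÷ 131.25 = 1.02.

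**4. How fast it shrinks.** Averages over d = 0 to 27, with every day weighted equally and every due dose given, for dosing every 1, 2 and 4 weeks:
- first cycle of a period: 182%, 280%, 489% (medians 127%, 156%, 208%);
- second cycle: about 110%, 120%, 140%;
- sixth cycle: about 102%, 105%, 110% (the weekly figure applies to dexamethasone only, since weekly elotuzumab ends after Cycle 2).

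The excess is nil if death falls exactly at the end of a dosing interval before the next dose. Weekly elotuzumab, death on Day 8 undosed: 7 × 10 ÷ 7 = 10, or 100%.

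**5. Role of the added day.** At d = 0 it replaces a zero denominator by 1. At d = 1 it does not apply, and the multiples are the same. At a later dose it lowers the result: weekly elotuzumab, second dose on the death date, gives 7 × 20 ÷ 7 = 20 without it and 7 × 20 ÷ 8 = 17.5 with it.

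**6. Effect on the tables.** One first-dose-day death among n subjects otherwise at plan moves mean elotuzumab DI by (70 − 10) ÷ n, (70 − 5) ÷ n or (140 − 5) ÷ n. With n = 200 (an assumption) that is 0.30, 0.33 or 0.68 mg/kg/week; 0.16 to 0.36 at n = 375 and 0.60 to 1.35 at n = 100. One value of 700% among 375 otherwise at exactly 100% gives a mean of 101.6% and a standard deviation of 31 points.

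Misclassification: a control subject given two of three due dexamethasone doses (67%) who dies at d = 15 scores 7 × 80 ÷ 15 ÷ 40 = 93%, in the top RDI category.

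**7. Elotuzumab RDI.** The SAP divides elotuzumab DI by PDI = (DOSE1 × 8 + DOSE2 × (DUR − 8)) ÷ DUR, not by the flat 10 or 5. With DOSE1 = 10, DOSE2 = 5 and DUR = 1/7 week, PDI = 285, so RDI is 70 ÷ 285 = 25% (Cycles 1-2 and 3) or 140 ÷ 285 = 49% (Cycle 19). At d = 7, PDI = 45 and RDI is 10 ÷ 45 = 22% (Cycle 3) or 20 ÷ 45 = 44% (Cycle 19). If the added day is not carried into DUR, a d = 0 death leaves PDI undefined.

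**The case against.** Cutting the clock at death has a rationale. Without it, a subject who died after one dose would be charged the full 28 days and score 0.25, 0.50 or 1.0 of plan, like a survivor who stopped after one dose. The extreme multiples need death on a period's first dosing day or the day after, so few subjects can show them. An adherent subject at 700% of flat plan belongs in the top RDI category anyway. Medians and quartiles are reported alongside the mean. All of this stands, and it limits the point to a minor one; it does not make the mean, standard deviation or maximum correct.

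Four stronger readings are tempting, and the documents do not support them.
- *The added-day sentence produces the 7, 14 and 28 multiples.* Death the next day gives the same values without it. The cause is the cut at death with doses counted whole, together with the period restarts.
- *Every adherent subject who dies shows more than 100%.* The undosed Day 8 death scores exactly 100%.
- *The error is always upward.* That fails for elotuzumab RDI, which the printed PDI formula puts at about 22-49% for such early deaths. That formula has a separate defect: for a full Cycles 3-18 period (DUR = 64) it gives 5.625, so a fully dosed subject scores 5 ÷ 5.625 = 88.9%.
- *The comparison of dexamethasone intensity between arms is compromised.* SAP 7.4.1.3 plans no test of it and both arms use the same cut at death. A distortion would need early on-treatment deaths to differ between arms.

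**Conclusion.** The point holds as a minor defect. For subjects who die within 28 days of the first dose of their last cycle, DI is generally overstated. The overstatement is large only in the first days of a period and modest from its second cycle on. The factors of 14 and 28 belong to elotuzumab alone.

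The consequence is confined to descriptive exposure tables: the mean, standard deviation and maximum of DI, and some top-category RDI entries for subjects who missed doses before death. No efficacy analysis uses these quantities.

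The figures assume dosing on the scheduled days and comparison with the stated flat weekly plans. The number of subjects who die this close to a period's first dose is not given, so the actual shift in any table is unknown.

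**What to change.** For a subject who dies before the first dose of the last cycle + 28 days:
- Compute RDI for the period as cumulative dose given ÷ cumulative dose scheduled before the death date. Add a dose due on the death date to the scheduled total only if it was given. For lenalidomide, count scheduled Days 1-21 doses only.
- Report DI as that RDI × the stated planned weekly dose for the period, so that the numeric summaries are corrected as well as the categories.
- Delete the added-day sentence.

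Check: death on the first dosing day gives 1 ÷ 1 = 100%; the undosed Day 8 death gives 1 ÷ 1 = 100%; two of three dexamethasone doses gives 67%. Counting an ungiven death-date dose as scheduled would instead score the Day 8 death at 1 ÷ 2 = 50%.

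The SAP should also say how a dose still inside its permitted window or delay at death is counted. The PDI formula needs its own correction; otherwise deaths and survivors would be on different elotuzumab RDI scales.

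Cost: SAP wording, slightly more programming and a separate rule for deaths. No new data are needed.
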